#### ***6.4.2 Local (Injection Site) Adverse Event Intensity***

Intensity of the following local injection site AEs should be assessed as described in **Table 5** adapted from the National Cancer Institute's Common Toxicity Criteria for Adverse Events version 4.03 (CTCAE v4.03).

**Table 5: Grading of Local (Injection Site) Adverse Event Intensity**

Local Reaction to Injectable Product	Absent (Grade 0)	Mild (Grade 1)	Moderate (Grade 2)	Severe (Grade 3)	Potentially Life Threatening (Grade 4)
Pain	Absent	Mild pain	Moderate pain; limiting instrumental ADL	Severe pain; limiting self-care ADL	Emergency room (ER) visit or hospitalization
Tenderness	Absent	Mild discomfort to touch	Discomfort with movement	Significant discomfort at rest	ER visit or hospitalization
Pruritus	Absent	Mild or localized	Intense or widespread; intermittent	Intense or widespread; constant	ER visit or hospitalization
Urticaria (hives, welts, wheals)	Absent	Urticarial lesions covering <10% Body Surface Area (BSA)	Urticarial lesions covering 10 - 30% BSA	Urticarial lesions covering >30% BSA	ER visit or hospitalization
Erythema/Redness *	Absent	Target lesions covering	Target lesions covering 10 - 30% BSA and associated with skin tenderness	Target lesions covering >30% BSA and associated with oral or genital erosions	Target lesions covering >30% BSA; associated with fluid or electrolyte abnormalities; ICU care or burn unit indicated
Induration/Swelling**	Absent	Mild induration, able to move skin parallel to plane (sliding) and perpendicular to skin (pinching up)	Moderate induration, able to slide skin, unable to pinch skin; limiting instrumental ADL	Severe induration, unable to slide or pinch skin; limiting joint movement or orifice (e.g., mouth, anus); limiting self-care ADL	Generalized; associated with signs or symptoms of impaired breathing or feeding

\* In addition to grading the measured local reaction at the greatest single diameter, the measurement should be recorded as a continuous variable.

\*\* Induration/Swelling should be evaluated and graded using the functional scale as well as the actual measurement.

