## 2.2 ENDPOINTS

### 2.2.1 Primary Endpoints

The primary endpoint of this study is to evaluate the safety and tolerability of DM199. Endpoints will be assessed as follows:

1. Safety:
  - Incidence, severity and causality of adverse events (AE) and serious adverse events (SAEs)
  - Physical examination changes from baseline (days 4, 22, 56, and 90)
  - Vital sign changes from baseline (resting heart rate, systolic/diastolic blood pressure, respiratory rate, and temperature) (days 1, 4, 7, 10, 13, 16, 19, 22, 56, and 90)
  - Hematology and chemistry parameter changes from baseline (days 4, 22, 56, and 90)
  - 12 lead ECG changes from baseline (days 1, 4, and 22)
2. Tolerability as assessed by incidence and severity of injection site adverse events.

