### 3.2 EXCLUSION CRITERIA

Potential subjects will be excluded from the study if any of the conditions apply:

1. Subject is currently prescribed angiotensin-converting-enzyme inhibitors (ACEi) and is unable or unwilling to convert to another antihypertensive pharmacological treatment for the duration of the study.

2. Subject has a history of significant allergic diathesis such as urticaria, angioedema or anaphylaxis.
3. Subjects with current malignancy or active malignancy  $\leq 5$  years prior to enrollment except basal cell or squamous cell carcinoma of the skin or in situ cervical cancer that has undergone potentially curative therapy and at least six months have elapsed since the procedure.
4. Subject has a history of clinically significant acute bacterial, viral, or fungal systemic infections in the last four weeks prior to enrollment.
5. Subject has clinical or laboratory evidence of an active infection at the time of enrollment.
6. Subject has known alpha 1-antitrypsin deficiency ( $\alpha 1$ -antitrypsin deficiency).
7. Subject has a known diagnosis of human immunodeficiency virus (HIV), hepatitis B surface antigen (HBsAg), or anti-hepatitis C virus (Anti-HCV) at screening.
8. Subject is pregnant or nursing.
9. Subject is male or female of childbearing potential, is participating in heterosexual sexual activity that could lead to pregnancy, and is unable or unwilling to practice medically effective contraception during the study.

*NOTE: Subjects should agree to use two reliable methods of contraception (e.g., double-barrier condom plus diaphragm, condom or diaphragm plus a stable dose of hormonal contraception) throughout the study period and until three months after receiving study treatment.*

*NOTE: A negative urine pregnancy test will be documented during screening.*

10. Subject is participating in any other drug study  $\leq 4$  weeks or 5 half-lives of the investigational product, whichever is longer.
11. Subject does not have sufficient venous access for infusion of study treatment or blood sampling.
12. In the opinion of the Investigator, subject is unlikely to be followed for the duration of the study.
13. Subject is unable or unwilling to comply with protocol requirements, including assessments, tests, and follow-up visits.
14. Subject has any other medical condition which in the opinion of the Investigator will make participation medically unsafe or interfere with the study results.

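### Table 5 grades local injection-site hives, redness and swelling partly by whole-body criteria, so Grades 2 and 3 by extent are out of realistic reach for local hives and redness

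*Combined protocol and SAP*

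**What the plan says.** Section 2.2.1 (repeated in 8.2.1) sets the second primary endpoint: "Tolerability as assessed by incidence and severity of injection site adverse events". Section 6.4.2 supplies the severity scale: "Intensity of the following local injection site AEs should be assessed as described in" Table 5, which is described as adapted from CTCAE v4.03.

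The rows at issue are these:

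- **Urticaria.** Grade 1 is below 10% of BSA, Grade 2 is "Urticarial lesions covering 10 - 30% BSA" and Grade 3 is "Urticarial lesions covering >30% BSA". Grade 4 is an emergency-room visit or hospital admission, with no surface condition.
- **Erythema/Redness.** Grade 2 requires target lesions over 10-30% of BSA with skin tenderness. Grades 3 and 4 require more than 30%, with mouth or genital erosions at Grade 3 and fluid or electrolyte disturbance at Grade 4.
- **Induration/Swelling.** Grades 1 to 3 rest on whether the skin can be moved and on function; Grade 3 includes "limiting joint movement or orifice (e.g., mouth, anus); limiting self-care ADL". Grade 4 is "Generalized; associated with signs or symptoms of impaired breathing or feeding".

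The * footnote, attached to Erythema, speaks of grading the local reaction by its largest diameter. The ** footnote, attached to Induration/Swelling, asks for grading by function and by actual measurement. Urticaria has no footnote.

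Section 4.5 withholds treatment at a Grade 3 or higher injection-site reaction and allows it to resume at Grade 0 or 1.

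**The concern.** A severity scale for local reactions should have grades that a local reaction can meet. If the middle grades of a row depend on the share of the whole body affected, a site that applies the table literally cannot call local hives or redness moderate or severe on extent, whatever it sees. The severity half of the tolerability endpoint then carries little information for these reactions.

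Local reactions are not a remote possibility here. Section 1.3 reports that eight of the 15 treatment-related events in the diabetes study were injection-site irritation, and each subject in this trial is to receive eight subcutaneous doses.

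There is also a boundary problem. A generalized reaction fits the wording of some upper cells, and 6.4.2 does not say when a widespread reaction stops being an injection-site event. The protocol treats such reactions as a concern at entry, since section 3.2 excludes anyone for whom "Subject has a history of significant allergic diathesis such as urticaria, angioedema or anaphylaxis". Two sites could label and grade the same event differently.

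**Working it through.** The plan states no figure to reproduce on this point. The check has three parts.

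**1. Scope against criteria.** Table 5 has six rows. Pain and Tenderness are graded by symptoms and function up to Grade 3 and by emergency-room visit or admission at Grade 4, so they have no whole-body criterion. Pruritus Grades 2 and 3 offer intensity as an alternative to spread, so a local itch can reach them. The other three rows (Urticaria Grades 2-3, Erythema Grades 2-4, Induration/Swelling Grade 4) contain criteria that are not local. The Erythema Grade 1 cell is incomplete in the text available to me and is not used.

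**2. How large are the surface cut-offs?** The inputs are the 10% and 30% cut-offs from Table 5. Total BSA is not in the protocol, so I assume 1.5 to 2.2 m². The diameter of a single circular patch covering fraction f of BSA is d = √(4 × f × BSA / π), with BSA in cm².

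| Assumed BSA | 10% area | Diameter | 30% area | Diameter |
|---|---|---|---|---|
| 1.5 m² | 1,500 cm² | 43.7 cm | 4,500 cm² | 75.7 cm |
| 1.8 m² | 1,800 cm² | 47.9 cm | 5,400 cm² | 82.9 cm |
| 2.2 m² | 2,200 cm² | 52.9 cm | 6,600 cm² | 91.7 cm |

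In the other direction, a patch of diameter d covers 100 × (π d² / 4) / BSA per cent:

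- 10 cm across: 78.5 cm², which is 0.52%, 0.44% and 0.36% of the three assumed BSA values.
- 20 cm across: 314 cm², which is 2.09%, 1.75% and 1.43%.

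Even a 20 cm reaction falls short of the 10% cut-off by a factor of about 5 (10 / 2.09 = 4.8) to 7 (10 / 1.43 = 7.0). Section 4.3 places injections in the lower abdomen, with the arms or thighs as alternatives. A reaction confined to any of these sites cannot realistically reach Grade 2 or 3 by extent. For hives the usable local grades are therefore 0, 1 and 4. For redness, Grade 4 also needs more than 30%, so Grades 2 to 4 are all out of reach by extent.

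**3. Table against its footnotes and users.** The footnotes presuppose diameter or measured size, but no cell in any row contains a length or a measured cut-off. The grades feed section 4.5 (withholding and resumption) and section 4.4, where persisting local pain, tenderness or swelling above Grade 1 prompts a change of site. The compression in Table 5 therefore passes into how those sections operate.

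**The case against.** Several things count against making more of this.

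- A reader might infer that local hives can never exceed Grade 1. That is wrong: Urticaria Grade 4 has no surface condition, so local hives that lead to an emergency-room visit or admission are Grade 4. The defect is the gap at Grades 2 and 3.
- A reader might infer that a systemic reaction filed as local is lost from safety, costing 1/33 = 3.0 percentage points of an arm's systemic hypersensitivity count. The protocol defines no such count. The safety endpoint covers all AEs and SAEs. Section 8.3.2.1 tabulates all treatment-emergent events by system organ class and preferred term, by maximum severity and at Grade 3 or higher, with listings, and has no separate injection-site table that could absorb an event.
- Section 6.3.2 asks for the diagnosis rather than component signs when one is available, so a recognised hypersensitivity event should be entered under its own name. Swelling with impaired breathing would very likely be an SAE under 6.2.2.
- For a treatment-related systemic reaction, section 4.5 applies at Grade 3 or higher under either label.
- The ACE-inhibitor ban is not evidence that the plan anticipates swelling or hives, because section 4.7 gives no reason for it. Only the allergic-history exclusion supports that reading.
- The analysis is descriptive (section 8.3), so no hypothesis test depends on these grades.

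All of this stands. It limits the boundary problem to inconsistent labelling and grading, not loss of data. It does not answer the grading problem: nothing elsewhere in the protocol supplies a usable moderate or severe grade for local hives or redness by extent. Adaptation from CTCAE does not help, because the scope was narrowed to local reactions while the whole-body descriptors stayed.

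**Conclusion.** The point holds as a defect in the scale. Three of six rows in a table restricted to local reactions use whole-body criteria, and the table does not match its own footnotes. For hives and redness, the smallest surface cut-off corresponds to a single patch about 44-53 cm across, and the next to about 76-92 cm. This rests on an assumed BSA of 1.5-2.2 m² and on treating the reaction as one circular patch; no plausible value in that range changes the conclusion.

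The consequence is compressed severity for these reactions within the primary tolerability endpoint, and grades in section 4.5 that inherit the compression. Pain and Tenderness are unaffected, Pruritus largely so, and the lower grades of Induration/Swelling still work. The possibility that a generalized reaction is graded as an injection-site event is real but secondary, since the event stays in the overall AE and SAE summaries. The text is wrong as written, not merely short of detail, and is cheap to correct.

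**What to change.** 1. In the Urticaria, Erythema/Redness and Induration/Swelling rows, replace the whole-body descriptors with local-extent and functional descriptors that agree with the * and ** footnotes, and extend the measurement requirement to Urticaria, which has no footnote now. The sponsor sets the cut-offs; none is proposed here.
2. Add to 6.4.2 a sentence to this effect: Table 5 is used only for signs confined to the injection site; a generalized reaction is recorded as a separate adverse event, graded under 6.4.1, and is not counted as an injection-site event.
3. Reconcile the revised Table 5 with section 4.5, because changing the rows changes which reactions meet its Grade 3 trigger. Which clinical rule should apply is for the sponsor to decide.

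The cost is three table rows, one sentence, a cross-check with 4.5 and brief site training. The small downside is that the revised grades would no longer follow the CTCAE skin terms, which makes comparison with trials using those terms less direct.

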### 6.4.3 Assessment of Causality

The Investigator or medically qualified designee is obligated to assess the relationship between investigational product and the occurrence of each AE. The Investigator or medically qualified designee will use clinical judgment to determine the relationship. Alternative causes, such as natural history of the underlying diseases, concomitant therapy, other risk factors, and the

temporal relationship of the event to the investigational product will be considered and investigated. The Investigator or medically qualified designee will also consult the Investigator's Brochure in the determination of his/her assessment.

There may be situations when a SAE has occurred and the Investigator has minimal information to include in the initial SAE report. However, it is very important that the Investigator (or medically qualified designee) always make an assessment of causality for every event prior to transmission of the SAE report form (refer to **6.5.1 Completion and Transmission of SAE Reports**). The Investigator or medically qualified designee may change his/her opinion of causality in light of follow-up information and amend the SAE report form accordingly. The causality assessment is one of the criteria used when determining global regulatory reporting requirements.

The Investigator will provide the assessment of causality utilizing one of four possible categories: Unrelated, Unlikely, Possible, and Probable.

- **Unrelated:** Clearly and incontrovertibly due to extraneous causes, and does not meet criteria listed under unlikely, possible or probable.
- **Unlikely:** Does not follow a reasonable temporal sequence from administration. May have been produced by the subject's clinical state or by environmental factors or other therapies administered.
- **Possible:** Follows as reasonable temporal sequence from administration. May have been produced by the subject's clinical state or by environmental factors or other therapies administered.
- **Probable:** Clear-cut temporal association with improvement on cessation of test drug or reduction in dose. Follows a known pattern of response to test drug.

## **6.5 EXPEDITED REPORTING OF SERIOUS ADVERSE EVENTS**

AEs meeting serious criteria **MUST** be reported promptly to the designated Sponsor CRO, and the local Institutional Review Board/Ethics Committee (IRB/EC). Prompt notification of SAEs by the Investigator is essential so that the Sponsor may comply with its global regulatory obligations.

### ***6.5.1 Completion and Transmission of SAE Reports***

Once an Investigator becomes aware that a SAE has occurred in a study subject, she/he will report the information on the SAE Report Form to the designated Sponsor contract research organization (CRO) within 24 hours. The SAE Report Form will always be completed as thoroughly as possible with all available details of the event and signed by the Investigator or medically qualified designee. If the Investigator does not have all information regarding the SAE, he/she will not wait to receive additional information before reporting the event but rather will update the SAE Report Form when additional information is received.

The Investigator or medically qualified designee will always provide an assessment of causality at the time of the initial report as described in **6.4.3 Assessment of Causality**.

Email transmission of the SAE Report Form is the preferred method to transmit this information to the designated Sponsor CRO. In rare circumstances notification by telephone is acceptable, however, notification via the telephone does not replace the need for the Investigator or medically qualified designee to complete and sign the SAE report form within the outlined time frame.

The Sponsor will provide a list of project contacts for SAE reporting including telephone, email, and fax numbers. Any event that in the opinion of the Investigator may be of immediate or potential concern for the subject's health or well-being will be reported to the Sponsor's Medical Monitor emergency contact.

### **6.5.2 Safety Unblinding**

If knowledge of treatment assignment is needed to manage a subject's condition, as in the case of an immediately reportable SAE, the Principal Investigator or designee will contact the Medical Monitor who, in consultation with the Sponsor, will grant permission to unblind the subject in accordance with the Unblinding Plan. The only exception is when a medical emergency exists and authorization cannot be immediately obtained.

If unblinding occurs, the date and reason for unblinding (but not the subject's treatment assignment) will be documented. Any subject who requires unblinding will be discontinued from further study treatment and an Early Withdrawal Visit will be completed. Subjects will not be routinely unblinded in the case of an AE.

### **6.5.3 Serious Adverse Event Reports to the IRB/EC**

The Investigator, or responsible person according to local requirements, will comply with the applicable local regulatory requirements related to the reporting of SAEs to regulatory authorities and the IRB/EC.

## **7 DATA COLLECTION AND MANAGEMENT**

### **7.1 DATA MANAGEMENT**

All required clinical data for this trial will be collected in web-based standardized electronic case report forms (eCRFs). FDA 21 CFR, Part 11 will be followed as well as other applicable legislation on the handling of electronic data. Subject personal information will be pseudonymized.

A Data Management Plan (DMP) will be developed outlining the procedures used for data review, database cleaning and issuing and resolving data queries. Procedures for validations and data storage will also be contained within the DMP.

Investigators and designated staff will receive training on eCRF completion and use of the electronic data capture (EDC) system prior to use.

## 7.2 SUBJECT IDENTIFICATION

After obtaining oral and written informed consent by the subject or his/her legally authorized representative, subjects will be screened according to the inclusion and exclusion criteria. If all eligibility criteria have been met, subjects will be randomized and enrolled into the study. Enrolled subjects will be assigned a unique subject number that will be used to identify them on source documents, eCRFs, and reports. Those who do not meet eligibility criteria or withdraw consent for any reason before completing all screening evaluations will be considered screen failures. Screen failures will not be entered in the eCRFs.

The Investigator or authorized designee at each site will keep a screening and enrollment log of all subjects screened and enrolled to document subject numbers and reasons for screen failures or withdrawals.

## 7.3 CASE REPORT FORMS

The Investigator is responsible for ensuring the accuracy and completeness of all study documentation. All protocol-required information collected during the study must be entered by the Investigator, or designated representative, in the eCRF. Each eCRF should be completed as soon as possible after data are collected, preferably on the same day the subject is seen for an examination, treatment, or any other study procedure and at the latest before the next monitoring visit. An explanation should be given for all missing data.

The completed eCRFs must be reviewed and signed by the Investigator named in the clinical study protocol.

## 7.4 SOURCE DOCUMENTATION

Original or certified copies of all relevant clinical findings, observations, and other activities throughout the clinical investigation must be recorded and maintained in the medical file of each enrolled subject. No source documentation will be recorded directly on the eCRF. Source documents may include, but are not limited to, admission/discharge records, lab and imaging reports, demographic records, and clinic visit records. A source data location list will be prepared prior to study start. This list will be filed in both the Trial Master File and the Investigator Study File and updated as necessary.

The Investigator will permit study-related monitoring, audits, IRB/EC review and authority inspections (refer to **12. Study Monitoring and Auditing**) by allowing direct access to all study records. In case of electronic source data, access must be allowed or dated print-outs must be available prior to the monitoring visits. Print-outs will not be limited to the treatment data only, but will include all available data related to the identified subject(s).

### **7.4.1 Source Documentation Reporting Requirements**

Images and corresponding reports for any brain imaging completed as part of standard of care treatment for any enrolled subject throughout the duration of the study (i.e. initial presentation through withdrawal) will be submitted to the CRO. In addition, it may be necessary from time to time to submit other source documents to the CRO or Sponsor to allow for timely safety discussions (i.e. expedited reporting of SAEs).

All source documents submitted to the Sponsor or its representatives, including imaging and reports, must be de-identified according to local and federal confidentiality requirements and identified by the subject number.

## **8 STATISTICAL CONSIDERATIONS**

### **8.1 STATISTICAL DESIGN AND SAMPLE SIZE**

#### **8.1.1 General Design**

This is a randomized, double-blind, placebo-controlled Phase II, multi-center study of DM199. Subjects presenting with acute ischemic stroke will be randomized 1:1 to placebo or DM199 administered by a single intravenous (IV) dose followed by subsequent subcutaneous (SC) doses.

